- **Adverse Events-** We will capture information on (1) changes in knee pain, swelling, and stiffness; (2) difficulty to bear weight on the surgical leg; (3) falls; (4) if subject has been hospitalized or disabled (> ½ day in bed or required to cut back on routine activities), and; (5) if subject had a TKR on the other knee. For information on falls we will ask subjects if they have had any falls using a 2-3 minute questionnaire developed at the Pittsburgh Pepper Center. One-week test-retest reliability (Kappa) was established as 0.89 in a sub-sample of 43 participants enrolled in a Pepper Center observational cohort study of older adults ([name] unpublished data). Falls will be defined as unintentionally coming to rest at a lower position. In this study serious adverse events (SAEs) are defined as hospitalization, death, or permanent disability. Adverse Events (AEs) are defined as exercise-related discomforts that remains for 3 days or longer (e.g., muscle and joint soreness/pain), minor injuries (e.g., strains, sprains), and non-injurious falls. Transient side effects are defined as complaints of increased pain, stiffness, or muscle weakness for periods of 2 days or shorter. We will compare the measures of harm such as adverse events and attrition by treatment interventions. If they differ between groups, they will be used as a covariate in the final outcome analysis.

We will also monitor attrition, adherence and co-interventions:

- **Attrition** is defined in this study as the number of patients dropping out of the study in each group.
- **Adherence** to intervention will be estimated by the proportion of sessions attended in each group and the proportion of patients missing each session. Adherence to the individualized outpatient exercise will be recorded by the physical therapist. Adherence to the group exercise classes will be obtained from reports generated by the community centers.
- **Co-interventions** will be queried during every assessment. Some subjects could decide to seek additional treatment options while enrolled in the study. We will ask about additional treatment sought (e.g., seeking specialized care), and participation in exercises besides the ones prescribed by the study. If the subject participated in additional exercises, we will record the frequency, duration, and type of the exercise and will analyze these data for their potential effect on the primary outcome.

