Interventions – The choice of comparators was based on concerns that patients, physicians, physician assistants, physical therapists, and community groups have about the interventions available to them.

Clinic-based individual outpatient rehabilitative exercise: Results of studies on the effectiveness of outpatient rehabilitative exercise at later stage post TKR appear to support this practice.⁸⁻¹¹ Yet, as the evidence is limited, clinicians only prescribe this intervention to a relatively small number of patients. All patients we interviewed unanimously said that outpatient exercise at later stage post TKR was essential to allow them to function at higher levels. Discussions with physicians indicated that they would feel more comfortable increasing the utilization of exercise at later stage post TKR provided there was stronger evidence about its benefits and risks. The exercise program that we will use in this group has been shown

PRINCIPAL INVESTIGATOR (LAST, FIRST, MIDDLE): [name]

to be safe and feasible, and combines the best research evidence from ours and other groups of investigators.⁸⁻¹¹ Details of the program have been published (<http://www.ncbi.nlm.nih.gov/pubmed/20378678>). Subjects will participate in 12 supervised sessions of exercise followed by a home exercise program. The 12 sessions will be delivered during 3 months in the following schedule: 2 sessions per week during weeks 1-3; 1 session per week in weeks 4 to 7; and 1 session every 2 weeks after that (in week 9 and 11). The gradual weaning will ensure that subjects learn the exercises, which helps increase adherence with the home exercise program. The home program mimics common rehab practice. Patients are instructed to perform at home the same exercises as in the clinic starting after the 3rd week of supervised intervention in a way that they exercise twice a week (either supervised exercise in the clinic or at home) during the 3-month intervention phase. Each exercise session will last about 60 minutes. Treatment sessions will utilize a pragmatic approach and will include the following components:

- Warm-up with stretching of lower extremity muscles and range of motion exercises;
- Moderate to vigorous intensity strengthening exercises of the major lower extremity muscle groups (knee extensors, knee flexors, hip extensors and hip abductors);
- Moderate intensity aerobic training using a treadmill or exercise bicycle;

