We will calculate dropout rates as proportions of subjects randomized and as a cumulative probability of remaining in the study using survival analysis techniques such as the product-limit estimator. This statistic can be estimated at various times following randomization and take into account when dropouts occur. Descriptive statistics will be used for reporting and evaluating implementation of the exercise protocols including the proportion in attendance for each session and the average number of sessions attended by group. The two intervention groups require the same number of exercise sessions (2 per week) for 3 months. To assess the impact of non-adherence, we could conduct a per-protocol analysis for the treatment effect but this would likely result in a biased estimate of the treatment effect due to selection bias of those who are more likely to adhere not representing a true random sample of trial participants. We propose to explore using instrumental variable methodology to estimate the efficacy for our interventions in the presence of non-adherence.⁹⁴ Instrumental variables have been mainly used in the econometrics⁹⁵ but have been proposed as a useful tool in estimating dose-response effects in psychological treatments where participants are expected to attend multiple sessions as part of the intervention protocol.⁹⁶ We propose to use the two-stage IV methods which can be easily implemented in Stata software using simple linear structural models for the effect of sessions attended on the primary outcome of function. We will also calculate the 6-month incidence (and 95% CI) of individual adverse events by organ system and relatedness to the study for each group. We will estimate the incidence of adverse events with specific focus on those deemed definitely, probably, or possibly related to interventions. For adverse events, clinical judgments will be considered more important than statistical testing.

Dropout and missing data analyses

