- Have a history of uncontrolled cardiovascular disease or hypertension;
- Are unable to walk 50 meters without an assistive device and to comfortably bear weight on the surgical knee;
- Have a history of muscular disease (e.g., muscular dystrophy) or neurological disorder that may affect lower extremity function (e.g., CVA, neuropathy, Parkinson's disease, multiple sclerosis);
- Regularly participate in structured exercise;
- Have a terminal illness;
- Are planning to have another joint replacement during the next 12 months;
- Do not plan to be around during the next 12 months (e.g., plan to travel, relocate to another city, etc.).

Inclusiveness of Different Populations- The make-up of the patient population of this study will be representative of the general population of older adults who undergo TKR in the US with respect to age, race, socioeconomic status, and general health. We will be sure to specifically target patients who provide important perspectives, such as patients who are ethnically diverse and have multiple chronic conditions or impaired access to healthcare because of age or disabilities. We will include subjects 60 or older because most patients undergo TKR after 60 years of age. While a higher number of patients are undergoing TKR at a younger age, they are still the minority and would be in better health than the older group. We did not impose an upper age limit for eligibility because many patients over 90 years undergo TKR. We believe that as long as they are cleared to do the surgery and they believe the TKR will be helpful to them, they should be in the study. Last, older patients who undergo TKR also have multiple comorbidities such as obesity, diabetes, high BP and arthritis of other joints^{19,20,101} and they will be included. Enrolling older adults with coexisting comorbidities will improve generalizability and clinical relevance of study results. With respect to race and socioeconomic status, we have been very successful recruiting an adequate proportion of African American and lower income research subjects and, as in the proposed study we will use similar recruitment strategies we expect similar success.

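### Adverse-event incidence is promised by organ system, but the plan describes only targeted questions and an exercise-related definition, so low or empty organ-system rows cannot be read as absence of harm

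*Combined protocol and SAP*

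**What the plan says.** **Reporting.** Under Exploratory Hypothesis in Data Analysis, the plan is to give each group's incidence over 6 months, with a 95% CI, for "individual adverse events by organ system and relatedness to the study". The same paragraph gives particular attention to events graded definitely, probably or possibly related, and ranks clinical judgment above statistical testing.

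**Collection.** In the Adverse Events part of Capturing Potential Harm of Interventions, the plan states: "We will capture information on (1) changes in knee pain, swelling, and stiffness; (2) difficulty to bear weight on the surgical leg; (3) falls". The list goes on to ask "if subject has been hospitalized or disabled (> ½ day in bed or required to cut back on routine activities" (the bracket closes there) and "if subject had a TKR on the other knee".

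**Definitions, same section.** Serious adverse events are hospitalisation, death or permanent disability. Adverse events are exercise-related discomforts lasting at least 3 days (muscle and joint pain are given as examples), minor injuries and non-injurious falls. Pain, stiffness or weakness lasting 2 days or less is a transient side effect.

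**Timing.** Table 1 schedules adverse events at the month 3 and 6 assessments and the month 1.5 and 4.5 calls. It adds nothing about what is asked.

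**The concern.** A table by organ system implies that every organ system was asked about. The described questions concern the knee, falls and activity-limiting illness, and the definition is tied to exercise. Palpitations, brief dizziness, breathlessness or a skin problem that does not make the patient cut back matches no listed item and does not clearly fit any definition.

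This matters because harms are part of the trial question in the Design Overview, and the plan says that monitoring will establish that the interventions do no harm. Participants are over 60, and the plan notes that "older patients who undergo TKR also have multiple comorbidities such as obesity, diabetes, high BP and arthritis of other joints". The clinic arm includes "Moderate to vigorous intensity strengthening exercises of the major lower extremity muscle groups" and moderate aerobic training. A row with few or no events and a narrow interval could be taken as evidence of safety for a system that nobody was asked about.

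**Working it through.** The documents give no adverse-event rate, sample size or power, so there is no figure of the plan's own to reproduce. The check is a comparison of collection with reporting, followed by an illustration.

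**1. Tracing kinds of event through the plan as described**

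| Event | Asked about? | Fits a definition? | Organ system recorded? |
|---|---|---|---|
| Knee symptom, fall | Yes | Yes, if exercise-related or a non-injurious fall; short-lived pain or stiffness counts as transient | Not described |
| Illness leading to hospitalisation | Yes, any cause | Serious adverse event | Not described |
| Illness causing more than half a day in bed or a cutback in activities, no hospitalisation | Yes, any cause | Neither adverse nor serious, unless exercise-related, an injury, or permanently disabling | Not described |
| Non-musculoskeletal event with no restriction of activity | No | Only if it counts as an exercise-related discomfort of 3 days or longer | Not described |

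The last row is the ascertainment gap. The third row shows a second gap: some events that are asked about have no clear route into the organ-system table.

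**2. Unequal opportunity to volunteer a report**

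All arms have the four scheduled contacts. The clinic arm adds 12 supervised sessions. The community arm adds classes twice a week, so 2 × 12 = 24 over 12 weeks. Usual care adds none, and the plan deliberately does not match attention. Unprompted reports would therefore tend to come from the exercise arms.

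**3. What an empty row would print**

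Inputs: 96, 96 and 48 randomised (Sample Size); 15% attrition at 6 months (Dropout and missing data analyses), so 96 × 0.85 = 81.6, about 82, and 48 × 0.85 = 40.8, about 41. The exact two-sided 95% upper limit for zero events is 1 − 0.025^(1/n).

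- 0/96: 1 − 0.025^(1/96) = 3.8%
- 0/48: 1 − 0.025^(1/48) = 7.4%
- 0/82: 4.4%
- 0/41: 8.6%

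These limits depend on n alone. They are the same whether everyone was asked and had no event, or nobody was asked.

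**4. Partial capture (incidence and capture are assumptions)**

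With true incidence p and capture probability c, the expected number recorded is 96·p·c, and the chance of an empty row is (1 − p·c)^96.

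| p | c = 100% | c = 50% | c = 25% | c = 0 |
|---|---|---|---|---|
| 5% | 4.8 expected; 0.007 | 2.4; 0.09 | 1.2; 0.30 | 0; 1 |
| 10% | 9.6; <0.0001 | 4.8; 0.007 | 2.4; 0.09 | 0; 1 |

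Partial capture reduces the shortfall without removing it, and the printed interval covers sampling error only.

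**The case against.** The strongest reply is that the gap is narrow and rests partly on silence. Most of this stands, and it limits what can be claimed.

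- **The list is not said to be exhaustive.** No adverse-event form is shown, volunteered reports are not ruled out, and the plan to classify by organ system may itself imply a fuller record. The text also points to a Human Subjects section that is not in the supplied document. So events may be missed; it cannot be said that they will go unrecorded.
- **The hospitalised-or-disabled question has a low threshold and no restriction on cause.** Many cardiac, respiratory or metabolic illnesses would be picked up in every arm. A reader might infer that non-musculoskeletal rows will be near zero by construction. This item is why the documents do not support that.
- **There are other routes.** Additional treatment sought is asked about at every assessment, under co-interventions, and class participants are watched for discomfort. Neither is described as feeding the adverse-event table.
- **A reader might infer that 0/96 would wrongly exclude a true rate of 5% or 10%.** That requires zero capture, and it sets a rate across all systems against a single-system row. An assumed 10% spread evenly over five systems is 10% / 5 = 2% each, which lies inside the 3.8% limit.
- **Safeguards exist.** Medical clearance is required; contraindications to exercise testing and uncontrolled cardiovascular disease or hypertension are exclusions; exercises start at low intensity. These may lower the event rate, but they do not make ascertainment complete.

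Targeted harm questions are a defensible choice in a pragmatic exercise trial. What they do not support is a table presented by organ system without qualification.

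**Conclusion.** The point holds in a limited form. The described collection does not support reading the organ-system incidence table as complete. Non-musculoskeletal events that leave activity unrestricted are not solicited, and some that are solicited have no clear place under the definitions. Reliance on volunteered reports would also favour detection in the exercise arms.

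The size of the loss is unknown, because the documents give no event rates. The upper limits of 3.8% for 0/96 and 7.4% for 0/48 illustrate the zero-capture extreme and are not a forecast. The conclusion assumes that no open question or organ-system coding is specified in material outside the supplied text.

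The analysis is exploratory and the primary endpoint is unaffected. It is still worth settling before data collection, since events that were never asked about cannot be reliably recovered later.

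**What to change.** **Preferred.** At the existing contacts (months 1.5, 3, 4.5 and 6), ask all three arms the same open question about any other new or worsened health problem. Record the organ system for each answer, and also for events reported under the hospitalised-or-disabled question. Then either align the adverse-event definition so that these events can be counted in the planned table, or tabulate them as a separate category. Without that step the new events would be collected but fall outside the plan's own definition.

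**Otherwise.** Remove the organ-system breakdown from the Exploratory Hypothesis analysis, and limit the harms conclusion to the solicited event types: knee symptoms, weight bearing, falls, hospitalisation or disability as defined, and replacement of the other knee.

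**Cost.** The first option needs one item on forms already in use, a simple coding scheme and a sentence in the definition. Its small downside is more minor, unrelated events to code. The second is a text edit.

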- For patient-reported function we will use the Western Ontario and McMaster Universities Osteoarthritis Index Physical Function Subscale (WOMAC-PF). The score at 3 months will be the primary end point. This instrument was developed based on patient input and is the instrument of choice to assess outcome post-TKR.⁵³ The WOMAC-PF consists of 17 items related to physical function. Each item is scored on a 5-point Likert-type Scale with descriptors from 0-4 (none, mild, moderate, severe, and extreme difficulty). Scores of each item are summed for a maximum total score on the WOMAC-PF of 68. Higher scores indicate worse functional limitations. Reliability and validity of this instrument have been established.⁵⁴⁻⁵⁶ Prior to choosing the WOMAC-PF as the primary outcome, we received input from patients. We asked for 15 patients post TKR to compare the WOMAC, the Lower Extremity Functional Scale (LEFS) and the Knee Outcome Survey (KOS). The patients observed that 4 activities of the LEFS (running on even ground, running on uneven ground, making sharp turns while running fast, and hopping) were not applicable as they are unusual and contra-indicated motions after TKR. They also noted that the focus on symptoms of pain and knee buckling of the KOS were not as relevant to them as the activities limitations queries in the WOMAC. Patients selected the WOMAC as the most patient-centered of the 3 instruments, but added that we should also test their true ability to perform tasks (see below).

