- For performance-based physical function we will measure a battery of 6 tests easily performed in the clinical setting. This selection was based on the interaction with hundreds of patients post-TKR in the last decade of work and during study design. During these interactions, patients expressed (and we observed) significant limitations in activities such as going up and down stairs, walking long distances, walking fast, balancing on one leg, and standing up from a chair. We will assess the performance of patients in all of these activities. During one of the planning meetings, patients also unanimously stated having difficulty getting up from the floor while gardening, cleaning the house and playing with their grandchildren and suggested that we include it as a test, which we did. So, the tests used in this study cover important domains of walking, dynamic and static balance, mobility, muscle strength and power, endurance, and coordination. These tests are reliable, responsive, and discriminate between low to high functional ability in older adults.^{42,57-62} Description of the tests follows: (1) Self-selected gait speed- measured in m/sec while patients walk at their regular pace over 4 meters. (2) Chair rise- seated in a chair (18" height) without armrests with arms crossed over the chest. Patients are timed during 5 repetitions of rising to a full upright position and sitting back down in the chair without assistance. (3) Single leg stance test – we will record the time of balancing on one leg while keeping the hands on the hips. The test lasts up to 60 sec and is stopped if the swing leg touches the floor, support foot moves on the floor, or arms swing away from the hips. (4) Stair ascend/descend test- patients will be timed while climbing up and down a set of 11 stairs (30 cm depth, 17 cm height) using a handrail on the preferred side. (5) Six min walk test-patients are instructed to cover as much distance as possible during 6 min with the opportunity to stop and rest if required. The test is conducted on an

PRINCIPAL INVESTIGATOR (LAST, FIRST, MIDDLE): [name]

unobstructed, rectangular circuit (marked in meters). (6) Sitting-rising test- it scores the ability of patients to sit and rise from the floor. Assistive devices will not be permitted during these tests.

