During our pilot study 100% of the patients completed the 2 month follow-up assessment;¹¹ however we are realistic and recognize that such retention rate is very optimistic for this study. Thus, in this study we estimate the attrition to be 10% at the 3 months follow-up. We also estimate the attrition to be 15% at 6 months, based on our pilot work and other studies with similar populations and timeframes. We will compare baseline characteristics between patients with and without the assessment at 3 and 6 months to assess potential biases in the complete case analysis. We will also try to obtain reasons for study drop out to assess the missing data mechanism (missing completely at random, missing at random, non-ignorable missingness). We will use several missing data methods for imputing data and re-analyze using intention to treat (as randomized) to assess the impact of missing data on our conclusions as recommended.⁹⁷ We

PRINCIPAL INVESTIGATOR (LAST, FIRST, MIDDLE): [name]

will first use multiple imputation (with M=10 imputations) which assumes the data are missing at random. Since the data could be missing not at random, we will use another approach of assigning the lowest observed scores for missing values differentially by treatment group (non-ignorable missingness). The approach assumes the missingness is directly related to the value of the missing data, i.e., the people who are missing data on function have worse function scores (did not come in for assessment because function was worse). Results of all approaches to missing data will be presented in the primary paper for our study. If our significance and interpretation of our treatment effect vary depending on the method of imputation, we will view any conclusions cautiously.

PATIENT POPULATION

Detailed reasoning of inclusion criteria is provided in Human Subjects.

Subjects will be included in the study if they underwent a unilateral TKR 2 to 4 months prior to study, are older than 60 years of age, experience functional limitation in daily activities (score in the WOMAC-PF of at least 9 points), *speak English sufficient to understand study instructions*, are willing to be randomized to one of the 3 treatment groups, and have medical clearance to participate in the study.

Subjects will be excluded if they:

- Have absolute or relative contraindications to exercise testing as established by the American College of Cardiology/American Heart Association;^{99,100}

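### The only missing-not-at-random analysis gives dropouts the lowest observed score, which on WOMAC-PF is the best function and contradicts its own stated assumption

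*Combined protocol and SAP*

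**What the plan says.** The section on dropout and missing data analyses plans multiple imputation under missing at random. It then adds a second approach for data that may be missing not at random (MNAR): "assigning the lowest observed scores for missing values differentially by treatment group (non-ignorable missingness"). The next sentence gives the rationale, that "the people who are missing data on function have worse function scores", because poor function kept them from attending. Results of every approach are to appear in the primary paper, and conclusions are to be viewed with caution if significance or interpretation changes with the method.

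The scale is defined under Outcomes, Physical Function: "Scores of each item are summed for a maximum total score on the WOMAC-PF of 68", and "Higher scores indicate worse functional limitations". For the same instrument, "The score at 3 months will be the primary end point".

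The performance tests in that section do not share one direction. For the chair rise, "Patients are timed during 5 repetitions of rising", and the stair test is also timed. Gait speed, six-minute walk distance and single-leg stance time are better when higher.

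**The concern.** The rule and its rationale point in opposite directions on the primary endpoint. If dropouts are assumed to function worse, they should receive a high WOMAC-PF score, but the plan gives them the lowest.

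This is the only MNAR analysis planned; the mixed model and the multiple imputation both rest on missing at random. Its job is to challenge a favourable result by supposing that those lost did badly. As written it supposes that they did as well as the best patient observed, so it rewards whichever arm loses more patients. It can reassure wrongly when the better arm has more dropout, and alarm wrongly when the worse arm does. Since the result is published and feeds the robustness judgement, a reader could be misled either way.

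**Working it through.** **Direction.** Three statements suffice. (a) Missing values receive the lowest observed score. (b) Missing patients are assumed to function worse. (c) On WOMAC-PF, higher is worse, so lowest is best. Under (c), rule (a) contradicts (b). No section reverse-codes the scale or exempts it from the rule.

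**Inputs from the plan.** 96 randomised per exercise arm and 48 to usual care; SD 7.7; design difference 3.3 points between the exercise arms and 5.2 against usual care; two-sided alpha 0.05 (all from Sample Size). For 3 months, "we estimate the attrition to be 10% at the 3 months follow-up".

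**The plan's own figure.** With 86 per arm, SE = 7.7 × √(2/86) = 1.174. Then 3.3/1.174 − 1.960 = 0.850, and Φ(0.850) = 80.2%, close to the stated 81%. Also 96 × 0.90 = 86.4. The sizing reproduces and is not in dispute.

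**Assumptions.** The plan gives no follow-up mean, so 3-month means of 12 to 20 are assumed. Dropout is random, each arm uses its own extreme, scores are limited to 0–68, and the comparison is unadjusted.

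**One arm.** The mean moves by d × (E − m), where d is the fraction missing, E the imputed score and m the observed mean. With 10 of 96 missing and m = 15.09 (the simulated mean):

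- lowest score, E ≈ 0.1: (10/96) × (0.1 − 15.09) = −1.56, an apparent improvement;
- highest score, E ≈ 33.8: (10/96) × (33.8 − 15.09) = +1.95, an apparent worsening.

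**Two arms, no true difference, 15% v 5% missing.** This is 14 v 5 of 96, a gap of 9/96.

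- lowest: (9/96) × (0.1 − 15.09) = −1.41, favouring the arm with more dropout;
- highest: (9/96) × (33.7 − 15.09) = +1.74, penalising it.

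Simulation (3,000 trials per setting) agrees:

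| Assumed mean | Lowest score: points in favour of the arm with more dropout | Highest score: points against it | Swing |
|---|---|---|---|
| 12 | 1.11 | 1.77 | 2.88 |
| 15 | 1.40 | 1.73 | 3.13 |
| 18 | 1.61 | 1.73 | 3.34 |

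At 10% v 10% missing, both shifts are about 0.

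**True 3.3-point difference; the better arm loses 15%, the other 5%.** With the worse arm's mean at 15 or 20, the literal rule gives an estimated advantage of 4.1 or 4.7 points, significant in 96% or 97% of trials. Highest-score imputation gives about 1.5 points, significant in 20% or 21%. The check strengthens the result it was meant to test.

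**True 5.2-point benefit over usual care; usual care loses 20%, exercise 10%.** With exercise means of 12 to 18, the literal rule cuts the estimate to 3.1–3.6 points and the worst-score rule raises it to 6.5–6.7. Here the error gives a false alarm.

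**The case against.** The best reply is that *lowest* is loose wording for *worst*: the next sentence makes the intent plain, and a sensible analyst would code it correctly. That shows which way to mend the rule, but does not make the rule right. Coded literally, it runs backwards; corrected silently, the published analysis departs from its plan.

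Second, this is a sensitivity analysis. The primary mixed model, its error rate and the sample size are unaffected, and caution is triggered by disagreement among methods, not by this one alone. All of that is true and limits the damage to the robustness check.

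Third, the size rests on a chosen dropout split. The plan assumes 10% in all arms, where the shift under no true difference is nil, and it does not predict 15% v 5% between the exercise arms. The shift scales with the gap: at 12% v 8%, four tenths as wide, 1.1–1.6 becomes about 0.4–0.6 points. This stands, and the figures are illustrative. Unequal dropout is nevertheless expected: the exploratory hypothesis predicts lower attrition in the exercise groups than in usual care. Overall, "We also estimate the attrition to be 15% at 6 months", so more values are at stake at that visit.

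Fourth, applying the rule separately by treatment group is not defined. The figures use each arm's own extreme; a pooled extreme gives the same direction.

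Finally, the scoring direction of the sitting-rising test is only inferred from its description as scoring ability, and the activity measures and performance composite also need a direction. These points concern completeness.

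**Conclusion.** The concern holds. On the primary endpoint the plan's only MNAR analysis does the opposite of what it says it assumes, and one unqualified *lowest* cannot suit outcomes that run in different directions. The direction of the error follows from the plan's text and needs no assumption.

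Its size is conditional. In the 15% v 5% scenario, the literal and intended analyses differ by 2.9 to 3.3 points, against a design difference of 3.3. That is a distance between two sensitivity results, not a bias in the primary estimate, and it shrinks to nil as dropout becomes equal under no true difference. It should still be corrected before analysis, because the check is published and used to judge how far the findings can be trusted.

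**What to change.** Replace the lowest observed score with the worst observed score and state the direction for each outcome:

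- highest observed value: WOMAC-PF, chair-rise time, stair time;
- lowest observed value: gait speed, six-minute walk distance, single-leg stance time, and the sitting-rising score once its scoring direction is confirmed;
- a stated direction for each physical-activity measure and for the performance composite, if the rule is applied to them.

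In the same edit, say whether the worst value comes from the patient's own arm or from all arms pooled. The cost is one sentence in the plan and one line of code per outcome; no data collection or sample size changes.
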